6.1.2. General Considerations for Analyses during Period 2 (Induction Dosing Period)

Period 2 starts after the first dose of study treatment (Visit 2, Week 0) and ends prior to the first injection of study treatment at Week 12 (Visit 7) or the early discontinuation visit (between Weeks 0 and 12). If a patient has Visit 7 but does not receive injection at Week 12 (Visit 7), the last recorded time for Visit 7 is used as the end time for Period 2.

Baseline for ITT and Safety Populations will be defined as the last available value before the first injection for efficacy, health outcomes, and safety analyses. In most cases, this will be the measure recorded at Week 0 (Visit 2). For efficacy/health outcome measures, if the patient does not take any injection, the last available value on or prior to randomization date will be used. Change from baseline (CFB) will be calculated as the visit value of interest minus the baseline value. For safety analyses using a baseline period, the baseline period is defined as the time from Visit 1 to the date/time of the first injection.

Comparisons between each ixekizumab treatment group (80 mg Q2W or 80 mg Q4W) and placebo will be performed for all analyses in Period 2.

The primary analysis method for treatment comparisons of categorical efficacy and health outcomes variables will be a logistic regression analysis with treatment as a factor using PROC Logistic. The odds ratio and the corresponding 95% CIs, as well as the treatment differences and the corresponding 95% CIs, will be reported. Secondary analysis will be conducted using a Fisher's exact test. In the case when logistic regression model does not produce statistical results due to sparse data, Fisher's exact test will be used.

For all categorical efficacy and health outcome variables that are collected at repeated visits, treatment group comparisons will be analyzed at each visit using the logistic regression model. Missing data will be imputed using the NRI method (Section 6.2.1).

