Age group at psoriasis onset	<40 years (Type 1 psoriasis), ≥40 years (Type 2 psoriasis)	
Duration of psoriasis ^e	quantitative summary (in years)	
Age at psoriasis diagnosis	quantitative summary (in years)	
Duration of psoriasis diagnosis ^f	quantitative summary (in years)	
Baseline sPGA	quantitative summary	
	category: 3, 4, 5	Yes
	category: 3, combined 4 or 5	Yes
Baseline PASI	quantitative summary	
	<20, ≥20	Yes
Psoriatic arthritis	yes, no	
Finger nail psoriasis	yes, no	Yes
Baseline NAPSI	quantitative summary	
Scalp psoriasis	yes, no	Yes
Baseline PSSI	quantitative summary	
Palmoplantar psoriasis	yes, no	Yes
Baseline PPASI	quantitative summary	

Baseline BSA (%)	quantitative summary	
	<20%, ≥20%	Yes
Baseline Itch NRS score	quantitative summary	
	<4, ≥4	
	=0, >0	
Baseline DLQI total score	quantitative summary	
	<5, ≥5	
Baseline Joint Pain VAS (for patients with baseline PsA)	quantitative summary	
Baseline QIDS-SR16	quantitative summary of total score	
	Item12: 0, 1, 2, 3	

Abbreviations: BMI = body mass index; UVB= ultraviolet B; PUVA= psoralen and ultraviolet A; QIDS-SR 16= Quick Inventory of Depressive Symptomatology–Self-Report 16 items.

^a Age will be calculated as: Age = floor((intck('month', brthdte, rfstdte) – (day(rfstdte) < day(brthdte)))/12). Here brthdte = Imputed date of birth (July 1st in the year of birth collected in the eCRF), and rfstdte = subject reference start date (that is, the date when patient is first exposed to study treatment).

^b BMI will be calculated as BMI (kg/m²) = Weight (kg) / (Height (m))².

^c Non-biologics are defined as: cyclosporine, methotrexate, corticosteroids, acitretin, fumaric acid derivatives, apremilast, other non-biologics, and psoralen and ultraviolet A (PUVA).

^d Biologics are defined as: efalizumab, ustekinumab, infliximab, etanercept, alefacept, adalimumab, golimumab, certolizumab pegol, and other biologics.

^e Duration of psoriasis = (date of informed consent – date of psoriasis onset)/365.25, where the date of psoriasis onset is recorded on the Prespecified Medical History – Psoriasis eCRF page.

^f Duration of psoriasis diagnosis = (date of visit 2 – date of psoriasis diagnosis)/365.25, where the date of psoriasis diagnosis is recorded on the Prespecified Medical History – Psoriasis eCRF page.

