	MMRM	Maintenance Dosing Period Primary Population	IXE80Q2W/IXE80Q4W vs. IXE80Q2W/PBO and IXE80Q4W/IXE80Q4W vs. IXE80Q4W/PBO and IXE/IXE vs IXE/PBO at all postbaseline visits in Period 3	Other secondary analysis (Section 6.9.4.2.1, Section 6.1.3.1)
NAPSI				
NAPSI score change from baseline	MMRM; ANCOVA with LOCF	ITT Population - patients with baseline nail involvement	IXE80Q2W & IXE80Q4W vs PBO at Week 12 and all other post-baseline visits in Period 2	Major secondary analysis (Section 6.9.2); Other secondary analyses (Section 6.9.4.1, Section 6.1.2)
	MMRM; ANCOVA with LOCF	Maintenance Dosing Period Primary Population with baseline nail involvement	IXE80Q2W/IXE80Q4W vs. IXE80Q2W/PBO and IXE80Q4W/IXE80Q4W vs. IXE80Q4W/PBO and IXE/IXE vs IXE/PBO at all postbaseline visits in Period 3	Other secondary analyses (Section 6.9.4.2.1, Section 6.1.3.1)
NAPSI score = 0	Logistic regression analysis with NRI; Fisher’s exact test with NRI	ITT Population - patients with baseline nail involvement	IXE80Q2W & IXE80Q4W vs PBO at Week 12 and all other post-baseline visits in Period 2	Other secondary analyses (Section 6.9.4.1, Section 6.1.3.1)
	Logistic regression analysis with NRI; Fisher’s exact test with NRI	Maintenance Dosing Period Primary Population with baseline nail involvement	IXE80Q2W/IXE80Q4W vs. IXE80Q2W/PBO and IXE80Q4W/IXE80Q4W vs. IXE80Q4W/PBO and IXE/IXE vs IXE/PBO at all postbaseline visits in Period 3	Other secondary analyses (Section 6.9.4.2.1, Section 6.1.3.1)
PSSI				
PSSI score change from baseline	MMRM	ITT Population - patients with baseline scalp involvement	IXE80Q2W & IXE80Q4W vs PBO at Week 12 and all other post-baseline visits in Period 2	Other secondary analyses (Section 6.9.4.1, Section 6.1.2)

Variable	Analysis Method (Sections 6.1 and 6.2)	Population (Section 6.1.1)	Comparison/Time Point	Analysis Type
	MMRM	Maintenance Dosing Period Primary Population with baseline scalp involvement	IXE80Q2W/IXE80Q4W vs. IXE80Q2W/PBO and IXE80Q4W/IXE80Q4W vs. IXE80Q4W/PBO and IXE/IXE vs. IXE/PBO at all postbaseline visits in Period 3	Other secondary analyses (Section 6.9.4.2.1, Section 6.1.3.1)
PSSI score = 0	Logistic regression analysis with NRI; Fisher’s exact test with NRI	ITT Population - patients with baseline scalp involvement	IXE80Q2W & IXE80Q4W vs PBO at Week 12 and all other post-baseline visits in Period 2	Other secondary analyses (Section 6.9.4.1, Section 6.1.3.1)

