	DLQI daily activities domain	Sum of responses of questions #3 and #4: #3. How much has your skin interfered with you going shopping or looking after your home or garden? #4. How much has your skin influenced the clothes you wear?	If one question in a domain is missing, that domain is missing.
	DLQI leisure domain	Sum of responses of questions #5 and #6: #5. How much has your skin affected any social or leisure activities? #6. How much has your skin make it difficult for you to do any sport?	If one question in a domain is missing, that domain is missing.
	DLQI work and school domain	Sum of responses of questions question #7A and #7B: #7A. Has your skin prevented you from working or studying? #7B. If No: how much has your skin been a problem at work or studying?	If the answer to question #7A is missing, this domain is missing. If #7A is No, and #7B is missing, this domain is missing.

Measure / Description	Variable	Derivation / Comment	Imputation Approach if with Missing Components
	DLQI personal relationships domain	Sum of responses of questions #8 and #9: #8. How much has your skin created problems with your partner or any of your close friends or relatives? #9. How much has your skin caused any sexual difficulties?	If one question in a domain is missing, that domain is missing.
	DLQI treatment	Response of question #10: #10. How much of a problem has the treatment for your skin been, for example by making your home messy, or by taking up time?	If one question in a domain is missing, that domain is missing.
	DLQI total score	A DLQI total score is calculated by summing all 10 question responses, and has a range of 0 to 30 (less to more impairment) (Finlay and Khan 1994; Basra et al. 2008).	If two or more questions are missing, the total score is missing. Note: #7B could be a valid missing while #7A is not “No.” That is, #7 should be considered as one question.
	DLQI (0,1)	A DLQI (0,1) response is defined as a post-baseline DLQI total score of 0 or 1. A DLQI total score of 0 to 1 is considered as having no effect on a patient’s HRQoL (Khilji et al. 2002; Hongbo et al. 2005).	Missing if DLQI total score is missing
	DLQI total score and domain scores change from baseline	Calculated as: observed DLQI (total score or domain scores) – baseline DLQI (total score or domain scores)	Missing if baseline or observed value is missing

Measure / Description	Variable	Derivation / Comment	Imputation Approach if with Missing Components

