
Joint Pain Visual Analog Scale (VAS): Joint Pain VAS is a patient-administered scale designed to measure current joint pain from psoriatic arthritis (PsA) using a 100-mm horizontal VAS. Overall severity of a patient’s joint pain from PsA at the present time is indicated by placing a single mark on the horizontal scale (0 = none; 100 = as severe as you can imagine).
	Joint Pain VAS	Range from 0 to 100. Note: higher value indicates greater severity of illness.	Single item, missing if missing
	Joint Pain VAS change from baseline	Calculated as: observed Joint Pain VAS – baseline Joint Pain VAS	Missing if baseline or observed value is missing
	Joint Pain VAS =0	Defined as a post-baseline Joint Pain VAS of 0	Missing if Joint Pain VAS is missing

Abbreviations: MCS = mental component summary; NRS = Numeric Rating Scale; PCS = physical component summary; PRO = patient reported outcome; SF-36 = Medical Outcomes Study 36-Item Short-Form Health Survey; VAS = visual analog scale.

Table RHBH. 6.7. Description of Health Outcomes and Quality-of-Life Analyses

Variable	Analysis Method (Sections 6.1 and 6.2)	Population (Section 6.1.1)	Comparison / Time Point
Itch NRS			
Itch NRS ≥ 4 improvement from baseline — Major secondary	Logistic regression analysis with NRI; Fisher's exact test with NRI	ITT population - patients with baseline Itch NRS score ≥ 4	IXE80Q2W & IXE80Q4W vs. PBO at Week 12 and all other post-baseline visits in Period 2
	Logistic regression analysis with NRI; Fisher's exact test with NRI	Maintenance Dosing Period Primary Population - patients with baseline Itch NRS score ≥ 4	IXE80Q2W/IXE80Q4W vs. IXE80Q2W/PBO, IXE80Q4W/IXE80Q4W vs. IXE80Q4W/PBO and IXE/IXE vs IXE/PBO at Week 60 and all other postbaseline visits in Period 3
Itch NRS change from baseline	MMRM	ITT population	IXE80Q2W & IXE80Q4W vs. PBO at Week 12 and all other post-baseline visits in Period 2
	MMRM	Maintenance Dosing Period Primary Population	IXE80Q2W/IXE80Q4W vs. IXE80Q2W/PBO, IXE80Q4W/IXE80Q4W vs. IXE80Q4W/PBO and IXE/IXE vs IXE/PBO at Week 60 and all other postbaseline visits in Period 3
DLQI			
DLQI (0,1)	Logistic regression analysis with NRI; Fisher's exact test with NRI	ITT population	IXE80Q2W & IXE80Q4W vs. PBO at Week 12 and all other post-baseline visits in Period 2

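### DLQI (0,1) response has no baseline condition, so patients who enter at 0 or 1 and stay there count as responders and dilute the Week 12 contrast (minor; an added restricted analysis would show it)

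*SAP*

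**What the plan says.** SAP Section 6.10, Table RHBH.6.6, gives the definition: "A DLQI (0,1) response is defined as a post-baseline DLQI total score of 0 or 1". The missing-data entry beside it, "Missing if DLQI total score is missing", also looks only at the post-baseline total.

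Table RHBH.6.7 analyses the variable by "Logistic regression analysis with NRI" and by Fisher's exact test. The Period 2 population is all ITT patients and the Period 3 population is the whole Maintenance Dosing Period Primary Population. SAP Section 6.1.2 describes the model as "logistic regression analysis with treatment as a factor using PROC Logistic", so baseline DLQI is not a covariate; Section 6.1.3.1 uses the same treatment-only model in Period 3. On effect measures, Section 6.1.2 says: "The odds ratio and the corresponding 95% CIs, as well as the treatment differences and the corresponding 95% CIs, will be reported".

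Protocol Section 8.1 requires BSA of at least 10%, sPGA of at least 3 and PASI of at least 12. It sets no DLQI minimum. SAP Table RHBH.6.3 summarises "Baseline DLQI total score" as a continuous variable and as below 5 or at least 5, with no 0-1 category.

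**The concern.** Table RHBH.6.6 itself treats a total of 0 or 1 as no effect on the patient's quality of life. A patient already there at Week 0 has nothing to gain on this variable, yet counts as a response if the score does not move. Low totals are possible despite extensive skin disease, because the SAP scores items marked not relevant as 0.

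Randomization spreads such patients over the arms, so they raise the response rate in each. If few other placebo patients reach 0 or 1, a handful of them can be a large part of the placebo responders, and the odds ratio is sensitive to that. The planned baseline categories would not show how many there were, so a reader of the results could not tell how much of either rate is unchanged status rather than improvement.

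**Working it through.** **The plan's own figures.** The documents give no expected DLQI (0,1) rate, no baseline DLQI distribution and no rate of staying at 0-1. The nearest stated figure is the co-primary power (SAP Section 5.3): 75% against 5%, 168 against 84 patients, two-sided Fisher's exact test at 0.025, power above 99%. Exact enumeration gives above 99.99%, so that figure reproduces. Its 5% placebo rate is for sPGA (0,1) and PASI 75 and cannot be carried over to DLQI.

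**Model.** Let q be the share with Week 0 DLQI of 0 or 1, p the response rate in the other patients of an arm, and r the chance that a baseline 0-1 patient is still at 0-1 at Week 12.

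- Observed rate in an arm = (1 - q)p + qr
- Odds ratio = odds of the observed active rate / odds of the observed placebo rate
- With r = 1 in both arms, risk difference = (1 - q)(p active - p placebo)

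**Full persistence (r = 1), assumed p = 60% active and 4% placebo.** Without such patients the odds ratio is (0.60/0.40)/(0.04/0.96) = 36 and the risk difference is 56 points.

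| q | Active rate | Placebo rate | Odds ratio | Baseline 0-1 patients among placebo responders | Risk difference (points) |
|---|---|---|---|---|---|
| 1% | 60.4% | 4.96% | 29 | 0.01/0.0496 = 20% | 55.4 |
| 3% | 61.2% | 6.88% | 21 | 0.03/0.0688 = 44% | 54.3 |
| 5% | 62.0% | 8.80% | 17 | 0.05/0.088 = 57% | 53.2 |

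For q = 3%: (0.612/0.388)/(0.0688/0.9312) = 1.577/0.0739 = 21. Of 84 placebo patients, 1%, 3% and 5% are 0.8, 2.5 and 4.2 people.

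**Other placebo rates, 60% active, r = 1.**

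| Placebo rate in the others | Odds ratio, q = 0 | q = 1% | q = 3% | q = 5% |
|---|---|---|---|---|
| 10% | 13.5 | 12.5 | 10.8 | 9.6 |
| 20% | 6.0 | 5.8 | 5.5 | 5.2 |

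**Incomplete persistence, 60% active.** With r = 0.9 active and 0.7 placebo:

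- Placebo 5%: odds ratio 28.5 becomes 25.4 at q = 1%, 22.9 at 2% and 17.8 at 5%. The risk difference at 5% goes from 55.0 to 53.2 points.
- Placebo 20%: 6.0 becomes 5.9, 5.8 and 5.5.

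With r = 0.9 active and 0.4 placebo, at 20% placebo response, the odds ratio stays at 6.0 for q up to 5%.

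**Power.** At 168 against 84 and two-sided 0.05, power stays at 99% or more in every scenario tried (active 50-70%, placebo 2-20%, q 1-10%).

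**Week 60.** SAP Section 6.1.3 makes patients who relapse and are retreated with ixekizumab non-responders for categorical variables, whatever their DLQI. Under Protocol Section 7.1.3, relapsing maintenance-placebo patients are the ones switched to ixekizumab. A patient with baseline DLQI 0-1 who relapses on placebo is therefore not counted as a responder, and the Week 12 calculation does not carry over.

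**The case against.** **The variable is a status, not a change.** The share of all randomized patients whose skin disease has no effect on quality of life is a legitimate ITT quantity. Improvement is already tested by the gated Test 9, DLQI change from baseline, with a baseline-adjusted MMRM. DLQI (0,1) carries no alpha and appears in no listed objective. This stands, and it is why the all-patient row should stay.

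**Other restricted populations are an imperfect precedent.** Table RHBH.6.7 limits the itch responder analysis ("ITT population - patients with baseline Itch NRS score" of at least 4), and Table RHBH.6.5 limits NAPSI = 0 ("ITT Population - patients with baseline nail involvement"). But a 4-point itch reduction is impossible from a lower start, and Protocol Attachment 1 has NAPSI and PSSI administered after baseline only to patients with nail or scalp disease. These limits follow from the measures, so they do not show that the SAP broke a rule of its own. They do mean that those analyses cannot count patients already at target, while DLQI (0,1) can.

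**The size is assumed.** A reader might infer that a few such patients would cut the odds ratio sharply. The documents do not support that. It needs placebo response of about 5% or less and near-complete persistence at 0-1, and neither is stated. The category below 5 in Table RHBH.6.3 does not show that 0-1 patients were expected. Non-responder imputation (SAP Section 6.2.1) also removes any with missing data. The treatment difference, reported beside the odds ratio, moves little.

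**The direction is mostly conservative.** Nothing here suggests a bias in favour of ixekizumab. That limits the harm, but it does not tell the reader how many responders were unchanged.

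**Conclusion.** The definition, the populations and the absence of a DLQI entry minimum together allow an unchanged patient to count as a responder; that rests on the text alone. The consequence at Week 12 is mainly dilution toward the null. The risk difference loses about the fraction q under full persistence. The fall in the odds ratio depends on the placebo rate: from 36 to 29 or 21 at 1% or 3% such patients with 4% placebo response, but only from 6.0 to 5.8 or 5.5 with 20%. All these DLQI rates are assumptions.

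It would be tempting to say the same of Week 60. The relapse rule breaks the assumption that such patients add equally to both arms, so the effect there is likely smaller, and no figure is offered. The gated DLQI test is unaffected, and power is not a concern. This is a minor point about how an ungated display will be read.

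**What to change.** In SAP Table RHBH.6.7, under DLQI (0,1), add for both periods an analysis in patients with a Week 0 DLQI total score above 1, by the same methods, shown beside the existing all-patient analysis. In Table RHBH.6.3, add a baseline DLQI category of 0-1, so that the number is reported per arm for the ITT population and for the Maintenance Dosing Period Primary Population.

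The cost is one subset flag on data already collected, one extra display per period, and a denominator in the added analysis that is smaller by the number of such patients. No gated test, sample size or objective changes. SAP Version 2 already revised one population in this table, for Joint Pain VAS, so an edit of this kind has precedent.

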6.11. Pharmacokinetic/Pharmacodynamic Methods

Details of pharmacokinetic/pharmacodynamic (PK/PD) analyses can be found in a separate PK/PD analysis plan.

6.12. Safety Analyses

Safety will be assessed by summarizing and analyzing AEs, laboratory analytes, vital signs, QIDS-SR16, and C-SSRS. The duration of treatment exposure will also be summarized.

Safety analyses will be conducted for each period separately, including Period 4 (Follow-up Period). Note that different baseline definitions will be used for each period (Section 6.1). All summaries of safety data for patients who experience relapse will use the relapse baseline (Section 6.1.3.3). Only treatment-emergent safety data will be summarized for the relapse population (that is, TEAEs including AESIs, SAEs, adverse events as reason for study treatment discontinuation, treatment-emergent clinical laboratory assessments, treatment-emergent vitals).

6.12.1. Extent of Exposure

Duration of exposure to study treatment will be summarized by treatment group for each treatment period using descriptive statistics.

6.12.1.1. Period 2 (Induction Dosing Period)

The duration of exposure on the induction dosing treatment for the Safety Population will be calculated as:

$$\begin{aligned} \text{Duration of induction exposure (days)} \\ &= \text{Date of last visit (scheduled or unscheduled) in Period 2} \\ &\quad - \text{Date of first dose in Period 2} + 1 \end{aligned}$$

The number and percentage of patients in each of the following categories will be summarized: >0 days, ≥7 days, ≥14 days, ≥30 days, ≥60 days, and ≥90 days. Note that patients may be included in more than one category. The number and percentage of patients falling into the following subcategories will also be summarized: >0 to <7 days, ≥7 to <14 days, ≥14 to <30 days, ≥30 to <60 days, ≥60 to <90 days and ≥90 days.

The summaries will also include the following information:

- Total exposure in patient years, calculated as:

$$\begin{aligned} \text{Induction exposure in patient years} \\ &= \frac{\text{Sum of duration of induction exposure for all patients in treatment group}}{365.25} \end{aligned}$$

- Mean and median total dose. Total dose (in mg) is calculated by the number of active injections taken during the treatment period multiplied by dose. For those patients randomized to 80 mg (Q2W or Q4W), the total dose (in mg) taken during Period 2 will be calculated as follows:

$$\begin{aligned} \text{Total Period 2 dose for patients on 80 mg (Q2W or Q4W)} \\ &= \text{Total number of active injections (including loading doses) received in Period 2} \\ &\quad \times 80 \end{aligned}$$

Note that the total number of active injections received will be calculated using the response to the question ‘Was dose administered?’ on the *Exposure as Collected* eCRF page and the actual dose description from IWRS study drug dispense dataset.

6.12.1.2. Period 3 (Maintenance Dosing Period)

6.12.1.2.1. Maintenance Dosing Period Primary Population and Maintenance Dosing Period Secondary Population

The duration of exposure on maintenance treatment will be calculated as:

$$\begin{aligned} & \textit{Duration of maintenance exposure (days)} \\ &= \textit{Date of last visit (scheduled or unscheduled) or relapse in Period 3} \\ & \quad - \textit{Date of first dose in Period 3} + 1 \end{aligned}$$

Note that patients who experience a relapse during Period 3 will only have their maintenance exposure calculated up until the date of relapse.

The number and percentage of patients in each of the following categories will be summarized: >0 days, ≥7 days, ≥14 days, ≥30 days, ≥60 days, ≥90 days, ≥120 days, ≥183 days, and ≥365 days. Note that patients may be included in more than one category. The number and percentage of patients falling into the following subcategories will also be summarized: >0 to <7 days, ≥7 to <14 days, ≥14 to <30 days, ≥30 to <60 days, ≥60 to <90 days, ≥90 to <120 days, ≥120 to <183 days, ≥183 to <365 days, and ≥365 days.

The summaries will also include the following information:

- Total exposure in patient years, calculated as:

$$\begin{aligned} & \textit{Maintenance exposure in patient years} \\ &= \frac{\textit{Sum of duration of maintenance exposure for all patients in treatment group}}{365.25} \end{aligned}$$

- Mean and median total dose (in mg). For those patients randomized to 80 mg Q4W, the total dose (in mg) taken during Period 3 will be calculated as follows:

$$\begin{aligned} & \textit{Total Period 3 dose} \\ &= \textit{Total number of active injections (including loading doses) received in} \\ & \quad \textit{Period 3 prior to relapse} \times 80 \end{aligned}$$

Note that the total number of injections received will be calculated using the response to the question ‘Was dose administered?’ on the *Exposure as Collected* eCRF page and the actual dose description from IWRS study drug dispense dataset.

